5.1.1.3 Definition of concomitant medication in case of missing dates

With respect to definition of medication as concomitant, the following rule will be applied in case of completely missing stop and/or start date information:

Medications with a missing start date whose stop date is either unknown or after the date of the first dose of LCM will be considered as concomitant medication. Medications with missing start date whose stop date is prior to first intake of LCM will not be considered concomitant.

In participant data listings, dates will be displayed as reported.

5.1.1.4 Incomplete dates for the last administration of LCM

For purposes of imputing missing components of partially reported dates for the last administration of LCM, the algorithms listed below will be followed. Stop dates of LCM will be displayed as reported in the participant data listings (ie, no imputed values will be displayed in data listing).

- Missing last administration day, but month and year present:

The last administration day will be set to the last day of the month or the date of the final contact, whichever is earlier in the month.

- Missing last administration day and month, but year present:

The last administration day will be set to the last day of the year or the date of the final contact, whichever is earlier in the year.

- Completely missing date of last administration:

For calculating the duration of exposure, if the date of last administration is completely missing and no information could be obtained from data cleaning exercises, the date of last administration should be imputed as the date of last contact according to the Study Termination eCRF module. For all other purposes, no imputation will be done if the date of last administration is completely missing.

If a participant died during the study, and the imputed last administration date according to the rules above is after the date of death, the last administration date will be assigned to the date of death.

5.1.1.5 General imputation rule for incomplete dates

Where necessary for the calculation of derived variables, partial dates will be completed using the earliest calendar date based on the partial date provided. This rule is valid for all partial dates with the exception of the following:

- Start and stop dates of AEs
- Start and stop dates of concomitant medication
- Start and stop dates of LCM

Completely missing dates will not be replaced and the corresponding derived variables will be set to missing.

5.1.2 General study level definitions

5.1.2.1 Analysis Time Points

5.1.2.1.1 First and last dose of LCM

Unless otherwise noted, all references to the first dose of LCM in this SAP refer to the first dose of LCM during EP0151 (ie, not the first dose of LCM from the previous study in which participants participated prior to EP0151). Unless otherwise noted, all references to the last dose of LCM in this SAP refer to the last dose of LCM in EP0151.

5.1.2.1.2 Relative day

Relative day will be calculated as the current date minus the date of first dose of LCM plus 1 for days on or after the day of first dose of LCM and prior to or on the day of last LCM dose (e.g., the day of first dose will be Day 1.) Relative day will be calculated as date of first dose of LCM minus the current date for days prior to the first dose of LCM (the day prior to first dose will be Day -1). For days after the last dose of LCM, relative day will be calculated as the current date minus the date of last dose of LCM including a “+” to denote posttreatment days (e.g., the day after the last dose will be Day +1). Relative day will not be calculated for partial dates or completely missing dates.

5.1.2.1.3 Study periods

This study consists of a Treatment Period and an End of Study Period.

Treatment Period

This is defined as the period of time from the date of first dose of LCM (Visit 1) to the Termination Visit for participants who complete the study or to the ETV for those who discontinued.

End of Study Period (Taper Period + Safety Follow-up Period)

This is defined as the period of time from the day after the end date of the Treatment Period and extending through to the Final Visit or last contact with the subject. No scheduled visits are planned in the Taper Period. Final Visit is the only scheduled visit in Safety Follow-up Period.

The maximum total duration of the study will be approximately 213 weeks, including an approximate 205-week Treatment Period and up to an 8 week Post-Treatment Period (4-week Taper Period and a Final Visit 30 days after the last dose). The end of the study is defined as the date of the last visit of the last study participant in the study.

5.1.2.1.4 End date of the Treatment Period

The end date of the Treatment Period will be either the date of Termination Visit for participants completing the Treatment Period, or the date of the Early Termination Visit (ETV) for participants who discontinued during the Treatment Period.

5.1.2.1.5 Mapping of assessments performed at Early Termination Visit

Safety assessments at an ETV that correspond to a scheduled visit will be summarized at the scheduled visit corresponding to the ETV if the assessment was scheduled to occur at that visit. If the ETV doesn't correspond to a scheduled visit, the assessment will be summarized at the next scheduled visit.

5.1.2.1.6 Definition of Baseline values

Baseline is defined as the last non-missing value collected prior to the first dose of LCM in the first LCM study. The Baseline values in EP0034 and SP0848 will be used as Baseline for safety variables in EP0151, if not stated otherwise. Visit 13/Termination Visit of EP0034 or SP848 will be Visit 1, Week 0 for EP0151. The vital signs measured after the 3 minute measurement in supine position of EP0034 at Visit 13/Termination Visit will be used as vital signs at Visit 1, Week 0 for EP0151.

5.1.2.1.7 Study visit labeling

Visits will be labelled in table summaries (according to the schedule outlined in Section 1.3 of the protocol) as follows:

- “Baseline”
- “Visit X, Week X” for scheduled visits during the Treatment Period
- “Termination Visit”
- “Last Visit”, which is the last non-missing assessment during the Treatment Period. All

scheduled and unscheduled assessments within this time period will be considered during the Treatment Period

- “Final Visit”

Listings will also include “Unscheduled Visit” and "Early Termination Visit" as applicable.

5.1.2.2 Body mass index (BMI)

BMI will be calculated using the formula:

$$\text{BMI} = \text{weight (kg)} / (\text{height [m]})^2$$

5.1.2.3 Exposure duration

The overall duration of LCM exposure for each participant will be calculated as the date of the last dose of LCM minus the date of the first dose of LCM plus 1 day. Gaps in treatment or days with unknown dosing will not be subtracted from the duration of exposure. The duration of LCM exposure will be summarized descriptively, separately, as a continuous parameter (in days) and as a categorical parameter, where categories will be defined using the following cumulative 6-month intervals for the Treatment Period: >0 months, >6 months, >12 months, >18 months, >24 months, >30 months, >36 months, >42 months, and >48 months, where 1 month is defined as 28 days.

Participant-years of LCM exposure in the study is calculated as the duration of exposure (days) divided by 365.25.

Participant-years of LCM exposure will be summarized using the following cumulative 6-month time intervals for the Treatment Period: >0 months, >6 months, >12 months, >18 months, >24 months, >30 months, >36 months, >42 months, and >48 months.

Participant-months of exposure will be calculated as the sum of days of exposure divided by 28.

5.1.2.4 Modal and maximum daily LCM dose

The modal daily LCM dose (mg/kg/day) is defined as the daily LCM dose the participant received for the longest duration during the Treatment Period in EP0151.

The maximum daily LCM dose (mg/kg/day) is defined as the highest total daily dose a participant received during the Treatment Period in EP0151.

Maximum daily LCM dose will be summarized as a continuous parameter (in mg/kg/day). Modal daily LCM dose will be summarized as a continuous (in mg/kg/day) and categorical parameter, using the following categories (mg/kg/day) for the Treatment Period: 0.0 to <4.0, ≥4.0 to <6.0, ≥6.0 to <8.0, ≥8.0 to <10.0, ≥10.0 to <12.0, and ≥12.0.

The modal and maximum daily dose calculations are based on the number of days a participant was on a given daily dose. Gaps in LCM dosing will be excluded from the determination of modal and maximum daily dose (i.e., no imputation for days with missing dosing log information will be performed). If a participant was on two different LCM doses for the same duration of time (i.e., a tie when calculating modal daily dose), the modal daily dose will be set to the lower of the doses.

In summary tables and listings, modal daily dose will be presented with the following column headers: <4mg/kg/day to represent doses from 0 to <4.0mg/kg/day, 4mg/kg/day to represent

doses 4.0 to <6.0mg/kg/day, 6mg/kg/day to represent doses 6.0 to <8.0mg/kg/day, 8mg/kg/day to represent doses 8.0 to <10.0mg/kg/day, 10mg/kg/day to represent doses 10.0 to <12.0mg/kg/day, and ≥12 mg/kg/day to represent doses greater than or equal to 12.0mg/kg/day.

5.1.2.5 Completer cohorts

A completer cohort will be defined as the subset of participants in the SS that were enrolled and treated with LCM for a specified duration of time. For example, a 12-month completer cohort consists of participants enrolled and treated with LCM for at least 12 months where a month is defined as 28 days.

Participants will be classified as belonging to one of the following completer cohorts for the purpose of subgroup analyses:

- 12 months
- 24 months
- 36 months
- 48 months

5.1.2.6 Protocol Deviations

Important protocol deviations are deviations from the protocol that could potentially have a meaningful impact on study conduct or on the key safety outcomes for an individual study participant. The criteria for identifying important protocol deviations and the classification of important protocol deviations will be defined within the appropriate protocol-specific document. To the extent feasible, rules for identifying protocol deviations will be defined without review of the data and without consideration of the frequency of occurrence of such deviations.

In general, protocol deviations will be considered according to the following general categories:

- Inclusion criteria
- Exclusion criteria
- Withdrawal criteria
- Prohibited concomitant medications
- LCM dosing regimen
- Procedural non-compliance

Important protocol deviations will be reviewed as part of the ongoing data cleaning process prior to database lock. A list of participants with important protocol deviations will be agreed upon during the Data Evaluation Meetings (DEM) and will be documented in the DEM minutes.

5.1.2.7 Treatment assignment and treatment groups

This is an open-label study; participants will not be randomized.

Where specified within this SAP, data will either be summarized by age group overall across all LCM doses or by modal daily dose (Section 5.1.2.4).

5.1.2.8 Center pooling strategy

No pooling of centers is planned for this study.

5.1.2.9 Coding dictionaries

Medical history and AEs will be coded using the Medical Dictionary for Regulatory Activities (MedDRA® v16.1). Medications will be coded using the World Health Organization Drug Dictionary (WHODD SEP/2013). Medical procedures will not be coded.

5.1.2.10 Hospital stay duration

The duration of each hospital stay will be calculated as the discharge date minus the admission date (Hospitalization/Emergency Room [ER] Visit Date on the eCRF module) plus 1 day for hospital stays with a discharge date.

5.2 Participant Disposition

The number of participants screened, and number and percentage of participants who were screen failures, broken down by primary reason for screen failure, will be presented for all screened participants.

The date of first participant in (date of earliest Visit 1 for this study), date of last participant out (date of final scheduled or unscheduled visit), number of screened participants, and the number of participants in SS, will be summarized overall and by investigator site. Participants who transfer sites will be summarized according to their original site.

A summary of disposition of analysis sets will be provided for all screened participants. The following will be summarized:

- The number and percentage of participants in the SS

Additionally, a summary of disposition and discontinuation reasons will present the following for all participants in the SS:

- The number and percentage of participants starting the study
- The number and percentage of participants completing the study
- The number and percentage of participants completing <12 months, ≥12 to <24 months, ≥24 to <36 months, ≥36 to <48 months, and ≥48 months where 1 month is defined as 28 days
- The overall number and percentage of participants discontinuing and the number and percentage of participants discontinuing by primary reason for discontinuation.

A summary of discontinuations due to AEs for SS will present the number and percentage of participants who discontinued from this study due to AEs broken down by type of AE.

The number and percentages of participants impacted by COVID-19 will be presented for each visit, overall and by impact category, for each relationship to COVID-19 as well as any relationship, overall and by country, for all participants in the SS. This will also be presented in the participant data listings. Relationship categories include confirmed COVID-19, suspected COVID-19, general circumstances around COVID-19 without infection, and Other. The table of

impact of COVID-19 for any reason includes only the events within the first three relationship categories.

5.3 Primary Endpoint(s) Analysis

In this open-label extension study, no statistical modelling will be used for analysis of the primary endpoints. The primary endpoints will be presented in descriptive statistics in the respective sections.

5.3.1 Definition of endpoints

TEAEs reported by the study participant or caregiver or observed by the Investigator

TEAEs will be defined as those events which started on or after the date of first dose of LCM in EP0151, or events for which severity worsened on or after the date of first dose of LCM in EP0151. AEs which occur within 30 days after final dose of LCM in EP0151 will be considered treatment-emergent.

Withdrawals from study due to TEAEs

Primary reason for premature study termination is collected in eCRF, one of which is AE. Together with the AE information for such participants collected in eCRF, early termination due to TEAE will be derived based on the definition of TEAE.

Withdrawals from study due to SAEs

The premature study termination due to AE collected in eCRF will be further considered for AEs indicated as serious in the eCRF.

Modal daily dose (mg/kg/day)

Definition of modal daily dose is in Section [5.1.2.4](#).

Maximum daily dose (mg/kg/day)

Definition of maximum daily dose is in Section [5.1.2.4](#).

5.4 Secondary Endpoint(s) Analysis

Not applicable.

5.5 Tertiary/Exploratory Endpoint(s) Analysis

Not applicable.

5.6 (Other) Safety Analyses

All safety variables will be analyzed by descriptive methods for the SS.

5.6.1 Extent of Exposure

The duration of LCM exposure (days), as defined in Section [5.1.2.3](#), will be summarized as a continuous parameter (in days). In addition, the duration of LCM exposure will be summarized using the cumulative 6-month time intervals for the Treatment Period, as defined in Section [5.1.2.3](#).

Participant-years of LCM exposure will be summarized using the cumulative 6-month time intervals for the Treatment Period, as defined in Section [5.1.2.3](#).

The maximum daily LCM dose (mg/kg/day), as defined in Section 5.1.2.4, will be summarized descriptively.

The modal daily LCM dose (mg/kg/day), as defined in Section 5.1.2.4, will be summarized descriptively. In addition, the number of participants and participant-years exposed in each of the modal daily LCM dose categories (mg/kg/day) will be summarized for the Treatment Period, as defined in Section 5.1.2.4.

Most recent study medication for PDILI will be listed for subjects in cases when PDILI occurred.

5.6.2 Adverse Events

AEs will be tabulated by MedDRA system organ class (SOC) and MedDRA preferred term (PT). The number and percentage of participants experiencing each event at least once will be summarized. All summaries will be sorted alphabetically by SOC and by frequency of events within PTs, starting with the most frequent event overall.

AEs will be classified as ongoing at entry, treatment-emergent and post-treatment. Ongoing AEs at entry are defined as AEs which had an onset date prior to the first EP0151 dose of LCM.

TEAEs will be defined as those events which started on or after the date of first dose of LCM in EP0151, or events for which severity worsened on or after the date of first dose of LCM in EP0151. AEs which occur within 30 days after final dose of LCM in EP0151 will be considered treatment-emergent. Post-treatment AEs are defined as AEs which had an onset date after 30 days after the last dose of LCM.

All AEs reported during the study including ongoing AE at entry and post-treatment AEs will be provided in a participant data listing. Ongoing AEs from EP0034 and SP848 will be followed up and reported in this study.

An overview of the incidence of TEAEs will provide the overall summary of TEAEs and the numbers and percentages of participants with at least 1 TEAE, with a serious TEAE, with a drug-related TEAE, with a severe TEAE. The number and percentage of participant discontinuations due to TEAEs, the number and percentage of all deaths (if applicable), and the number and percentage of participants with TEAEs leading to death (if applicable) will also be summarized.

The number and percentage of participants who discontinued due to SAE (regardless of treatment emergent) will also be summarized.

The following summaries of AEs will be provided by MedDRA primary SOC and PT:

- Incidence of TEAEs
- Incidence of serious TEAEs
- Incidence of non-serious TEAEs
- Incidence of ongoing AEs at EP0151 study entry
- Incidence of TEAEs leading to discontinuation
- Incidence of SAEs leading to discontinuation
- Incidence of TEAEs related to potential drug-induced liver injury (PDILI) (defined in

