## **9.3        Planned safety analyses**

### **9.3.1      Safety analyses**

Treatment-emergent AEs will be defined as those events which started on or after the date of first dose of LCM in EP0151, or events for which severity worsened on or after the date of first dose of LCM in EP0151. Adverse events which occur within 30 days after final dose of LCM in EP0151 will be considered treatment-emergent.

Adverse events will be coded using the Medical Dictionary for Regulatory Activities® (MedDRA). Pretreatment AEs, TEAEs, non-serious TEAEs, withdrawals due to TEAEs, withdrawals due to SAEs, and SAEs will be tabulated by system organ class and preferred term. The incidence of TEAEs will also be summarized by intensity and by relationship to LCM. In addition, all AEs will be listed.

Long-term use of LCM will be assessed by modal daily dose (mg/kg/day) and maximum daily dose (mg/kg/day). These doses will be summarized using descriptive statistics, along with duration of exposure (days).

Actual measurements and changes from Baseline in vital signs, body weight, height, and calculated BMI will be summarized descriptively by visit. In addition, shift tables may be used to evaluate the number and percent of study participants having a different post-Baseline status when compared with their Baseline status.

The endpoints for assessment of long-term use include TEAEs, study participant withdrawals due to TEAEs and SAEs, modal daily dose, and maximum daily dose. Available data related to these measurements will be presented in participant data listings.

Responses to the C-SSRS will be presented in participant data listings.

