5 STATISTICAL ANALYSES

5.1 General Considerations

Statistical analysis and generation of tables, figures, participant data listings, and statistical output will be performed using SAS Version 9.4 or higher. All tables and listings will use Courier New font size 9.

Descriptive statistics will be displayed to provide an overview of the study results. For categorical parameters, the number and percentage of participants in each category will be presented. The denominator for percentages will be based on the number of participants appropriate for the purpose of analysis. Unless otherwise noted, all percentages will be displayed to 1 decimal place. No percentage will be displayed for zero counts, and no decimal will be presented when the percentage is 100%. For continuous parameters, descriptive statistics will include number of participants (n), mean, standard deviation (SD), median, minimum, and maximum.

Decimal places for descriptive statistics will always apply the following rules:

- “n” will be an integer
- Mean, SD, and median will use 1 additional decimal place compared to the original data
- Minimum and maximum will have the same number of decimal places as the original value

All summaries, unless otherwise stated below, will be presented overall for all participants and additionally based on the participant’s age at time of entry into study EP0151, using the following age groups:

- ≥ 2 to <4 years
- ≥ 4 to <6 years

All summaries will be descriptive; no statistical hypothesis testing is planned.

Only scheduled visits will be included in summaries. A complete set of listings containing all documented data including scheduled and unscheduled and all calculated data (eg, change from Baseline) will be generated, and will be sorted by site, participant number and visit (where applicable). Study participant numbers that were utilized in SP848 and EP0034 will continue to be used in EP0151.

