Appendix 6.1.7)

- Incidence of TEAEs by relationship to LCM
- Incidence of fatal TEAEs by relationship to LCM
- Incidence of non-serious TEAEs by relationship to LCM
- Incidence of non-serious TEAEs occurring in at least 5% of participants
- Incidence of TEAEs by maximum intensity
- Incidence of other significant TEAEs (defined in Appendix 6.1.6)
- Incidence of drug-related TEAEs by seriousness
- Incidence of TEAEs by 100 participant-months of exposure. The event rates are derived using the total number of TEAEs, including unique and non-unique TEAEs, divided by the participant-months exposed, and multiplied by 100.

In addition, summaries for the incidence of TEAEs overall, incidence of serious TEAEs, incidence of TEAEs leading to discontinuation, incidence of SAEs leading to discontinuation, TEAEs related to PDILI, other significant TEAEs, and pediatric growth-, neurodevelopment-, behavior-, and endocrine-related TEAEs will be repeated presenting the site and participant number of all those participants experiencing each TEAE as well as in participant data listings. Pediatric growth-, neurodevelopment-, behavior-, and endocrine-related TEAEs will be determined by manual medical review of reported MedDRA PTs.

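### Withdrawals due to TEAEs and due to SAEs, two of the five primary endpoints, are planned only as n (%) overall and by entry age, although potential follow-up is systematically longer in the younger group unless regional approval comes early

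*SAP*

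**What the plan says.** Protocol section 3 and SAP 1.1 list five primary endpoints. Two of them are withdrawals from study due to TEAEs and due to SAEs.

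- SAP 5.6.2, TEAE withdrawals: "The number and percentage of participant discontinuations due to TEAEs".
- SAP 5.6.2, SAE withdrawals: "The number and percentage of participants who discontinued due to SAE (regardless of treatment emergent) will also be summarized".
- SAP 5.2: a disposition table "will present the number and percentage of participants who discontinued from this study due to AEs".
- SAP 5.3 adds no further method: "The primary endpoints will be presented in descriptive statistics in the respective sections".
- Protocol 9.3.1 asks only for tables: "withdrawals due to TEAEs, withdrawals due to SAEs, and SAEs will be tabulated by system organ class and preferred term".
- SAP 5.1 sets the layout: "All summaries, unless otherwise stated below, will be presented overall for all participants and additionally based on the" child's age at entry to EP0151, in two groups, 2 to under 4 and 4 to under 6 years.
- The one exposure-adjusted adverse event summary, in SAP 5.6.2, concerns all TEAEs: "The event rates are derived using the total number of TEAEs, including unique and non-unique TEAEs, divided by the participant-months exposed".

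Protocol 4.1 (Termination Visit) says when a child completes: at 6 years of age, or when the drug is approved for under-4s in the region and the oral solution is available, whichever is first. The Termination Visit is then held at the next scheduled visit. Visits are about every 26 weeks. The sponsor may allow longer treatment case by case.

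SAP 5.1.2.5 defines completer cohorts at 12, 24, 36 and 48 months, but no output is assigned to them, and SAP 5.8 plans no other subgroup analyses.

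**The concern.** The variable that defines the two columns, age at entry, also sets how long a child can be followed. To the sixth birthday, the younger group has more than 2 and up to 4 years, and the older group at most 2 years. A percentage ever withdrawn rises with time at risk, so with the same underlying risk the younger column is expected to show the higher figure.

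A reader of the study report could take that as poorer tolerability in younger children. The overall percentage has a milder form of the same problem, because it shifts with the mix of entry ages and with the date of approval. No planned output gives withdrawal incidence at a time point common to both groups.

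**Working it through.** **Inputs from the documents.** Age groups (SAP 5.1); completion rule and next-visit rule (Protocol 4.1); 26-week visits with a window of 7 days either side (Protocol Table 1-1); 28-day month and 365.25-day year (SAP 5.1.2.3); 80 to 100 children expected (SAP 3).

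**Assumptions, because the documents give no figure.** Entry age spread evenly within each group; the same withdrawal hazard in both groups; no extension past age 6; 45 children per group; approval times as shown.

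**1. The plan's own duration.** 205 + 8 = 213 weeks, as stated. Entry at 2 gives (6 − 2) × 52.18 = 208.7 weeks to the sixth birthday, close to the stated 205.

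**2. Potential follow-up, no early approval.** Time to the sixth birthday, rounded up to the next 26-week visit, falls in about equal quarters at 2.5, 3, 3.5 and 4 years (younger) and 0.5, 1, 1.5 and 2 years (older). The means are 3.25 v 1.25 years.

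**3. Crude percentage, constant hazard h = 0.05 per year.** Percentage = 1 − mean of exp(−hT).

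- Younger: 1 − (0.8825 + 0.8607 + 0.8395 + 0.8187)/4 = 15.0%.
- Older: 1 − (0.9753 + 0.9512 + 0.9277 + 0.9048)/4 = 6.0%.
- The ratio is 2.5. Capping follow-up at 205 weeks changes 15.0% to 14.9%. At hazards of 2 and 10 per 100 the ratio is 2.5 and 2.4.

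**4. Effect of approval.** Follow-up then ends at the first visit at or after the earlier of the birthday and approval (ratios from unrounded percentages):

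| Approval after entry | Mean years, younger v older | Crude %, younger v older | Ratio |
|---|---|---|---|
| None | 3.25 v 1.25 | 15.0 v 6.0 | 2.5 |
| 3 years | 3.12 v 1.25 | 14.4 v 6.0 | 2.4 |
| 2 years | 2.49 v 1.25 | 11.7 v 6.0 | 1.9 |
| 1 year | 1.49 v 1.12 | 7.2 v 5.4 | 1.3 |
| 0.5 year | 1.00 v 0.87 | 4.9 v 4.3 | 1.1 |

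**5. Does a rate per participant-year remove the difference?** With a constant hazard, yes: 5.0 v 5.0 per 100 in every row. With a front-loaded hazard (10 per 100 for six months, then 3; no early approval), the crude figures are 12.4% v 7.0% but the rates are 4.1 v 5.9, so the artefact reverses.

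**6. Does cumulative incidence at a fixed time?** Six SAP months is 6 × 28 = day 168, before the earliest completion visit (26 × 7 − 7 = day 175). Twelve SAP months is day 336.

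- Constant hazard: 1 − exp(−0.05 × 168/365.25) = 2.3% and 1 − exp(−0.05 × 336/365.25) = 4.5% in each group.
- Front-loaded hazard: about 4.5% and 6.1% in each group.
- Share whose potential follow-up reaches day 168, 336 and 672 (24 SAP months), no early approval: 100%, 100% and 100% (younger) v 100%, 75% and 25% (older).

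**7. Precision.** At 45 per group, constant hazard and no early approval, expected withdrawals are 45 × 0.150 = 6.8 v 45 × 0.060 = 2.7. By day 168 about 45 × 0.0227 = 1 event per group is expected, with a 36% chance of none (0.9773^45). At day 336 about 43 v 32 remain at risk, and the simulated 95% sampling range of the estimate is 0 to 11% v 0 to 12%. At day 672 about 41 v 10 remain.

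**The case against.** The study has one objective, long-term use. It tests nothing, and no age contrast is an objective or endpoint. The age columns come from a default layout, and n (%) is a correct report of how many children withdrew. Much of the context is already planned by age group: days of exposure and participant-years (SAP 5.1.2.3 and 5.6.1), disposition by time completed (SAP 5.2), and TEAEs per 100 participant-months (SAP 5.6.2). A careful reader could divide withdrawals by participant-years. All of this stands, and it limits the point to presentation.

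The size is also hypothetical. Hazard, age mix, group sizes and approval date are all assumed, and case-by-case treatment past age 6 could blur the contrast. This stands too. The structural difference in potential follow-up does not depend on those inputs, except on approval not coming early.

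The front-loaded scenario is not suggested by the documents: these children have completed a parent study on the drug and may keep their dose. So a rate per participant-year is a reasonable first addition. The scenario shows only that the rate needs a caveat and a fixed-time companion.

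Finally, the added estimates will be imprecise. That is true, but crude percentages from the same few events are no more reliable.

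**Conclusion.** The point holds as a reporting gap. Two primary endpoints will appear side by side by age as percentages that reflect different lengths of follow-up, with no withdrawal rate or fixed-time incidence planned. Under the stated assumptions, equal risk would appear as about 15% v 6% with no early approval, and as a ratio of about 1.3 or 1.1 if approval comes 1 or 0.5 years after entry.

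A reader might infer more than the documents support:

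- That the plan makes a biased comparison of tolerability by age. It makes none; the columns are descriptive and untested.
- That a 2.5-fold difference should be expected. It is one end of a range that rests entirely on assumed inputs.
- That exposure is ignored. It is tabulated by age, but not linked to withdrawals.
- That incidence should be compared by age at 24 months. Only about a quarter of the older group could reach that point, those entering at about 4 to 4.5 years, so the older column would no longer represent its group.

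**What to change.** In SAP 5.6.2, keep the n (%) and add the following for both withdrawal endpoints, overall and by age group:

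- **Rate.** Withdrawals per 100 participant-years, using the definition in SAP 5.1.2.3, with a note that it compares fairly across age groups only if the hazard is roughly constant over time.
- **Cumulative incidence (Aalen-Johansen)** at 6 and 12 SAP months of 28 days, with numbers at risk. Time runs from first EP0151 dose to the end of the Treatment Period as SAP 5.1.2.1.4 defines it ("The end date of the Treatment Period will be either the date of Termination Visit for participants completing the Treatment Period", otherwise the Early Termination Visit), or to last contact if there was no such visit. Censor at protocol-defined completion and at sponsor or site closure (Protocol 10.1.7), which is administrative. Treat other participant-level discontinuations as competing events. The 6-month figure needs no censoring for completion; the 12-month figure assumes that risk within an age group does not depend on entry age.
- **24 months.** If wanted, overall or for the younger group only.
- **Footnote.** Crude percentages by age group reflect different lengths of follow-up and are not a comparison of tolerability.

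The cost is SAP wording and one or two extra tables from data already collected (termination reason, Treatment Period dates). No protocol change is needed. The downside is wide intervals, because few events are expected.
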